4.2 Protocol Deviations

Subjects who did not meet the eligibility criteria for study entry but enrolled in the study will be summarized. The number and percentage of subjects who did not meet at least 1 eligibility criterion will be provided by treatment and cohort for each specific criteria based on the Randomized Set. A by-subject listing will be provided for those subjects who did not meet at least

1 eligibility (inclusion or exclusion) criterion. The listing will present the eligibility criterion (or criteria if more than 1 deviation) that subjects did not meet and related comments, if collected.

Protocol deviations (PDs) occurring after subjects entered the study are documented during routine monitoring. The number and percentage of subjects with important PDs (IPDs) by deviation category will be summarized by treatment and cohort for the Randomized Set. A by-subject listing will be provided for those subjects with any PDs.

A table will be provided to summarize any COVID-19 related PDs with the deviation reason by treatment and cohort. A listing of subjects who had study disruption due to COVID-19 will be provided with a description.

4.3 Extent of Study Drug Exposure and Compliance

Extent of exposure to study drug will be examined by assessing the total duration of exposure to study drug and the level of compliance relative to the study drug regimen specified in the protocol. Summary tables will be provided.

4.3.1 Duration of Exposure to Study Drug

Total duration of exposure to study drug will be summarized. Total duration of exposure will be defined as the last dose date of study drug minus the first dose date plus 1. If the last study drug dose date is missing, the latest date among the study drug end date, clinical visit date, laboratory sample collection date, and vital signs assessment date that occurred during the On-Treatment Period will be used for subjects included in the final analyses or the last available date in the database snapshot for subjects who were still on treatment at the time of an interim analysis.

The total duration of exposure to study drug will be summarized using descriptive statistics. Summaries will be provided by treatment and cohort for the Safety Analysis Set. The expected total duration of exposure is 1 day for subjects in Part A and 8 days for subjects in Part B.

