3.2.2 Secondary Endpoints

The secondary endpoints are:

- Noncompartmental plasma PK parameters such as AUC_{last} , AUC_{0-inf} , AUC_{tau} , C_{max} , T_{max} , C_{trough} , k_{el} , $t_{1/2}$, CL/F , V_z/F , dose normalized AUCs and C_{max} , accumulation ratios and linearity factor (as applicable for each part)
- Comparison of AUC and C_{max} between fasted and fed treatments (Part A, SAD, food effect cohorts only)

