10.4 Planned Analyses

All safety and PK endpoints will be summarized using descriptive statistics by treatment. Continuous endpoints will be described using the mean, standard deviation, median, minimum, and maximum. Categorical endpoints will be described using the number and percent of subjects who meet the endpoint criterion. The safety and PK analyses will be presented according to the treatment received. Due to sample size limitations, no formal statistical inference is planned.

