10.4.4 Analysis of Safety Endpoints

The safety parameters to be assessed are described in [Section 8.3](#). Displays for safety results will utilize descriptive statistics. No formal hypothesis testing of safety data is planned.

Adverse events will be coded using the Medical Dictionary for Regulatory Activities (MedDRA). A treatment-emergent adverse event (TEAE) will be defined as any AE that has an onset date or worsening in severity from Baseline on or after the first dose of study drug through end of study (defined in [Section 4.5](#)). Incidence of each body system and preferred term will be tabulated for each treatment. Summaries will include all TEAEs, TEAEs considered related to study treatment by the Investigator, graded TEAEs, serious TEAEs, TEAEs leading to premature discontinuation from the study intervention. All AEs, emergent or nonemergent, will be listed by subject.

Clinical laboratory results will be summarized descriptively by treatment including values, changes from Baseline, and incidence of laboratory abnormalities. Laboratory results will be listed for each subject.

Vital signs data and ECG findings reported at each visit will be displayed by treatment, using descriptive statistics for observed and change from Baseline values.

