The DRC will select a single dose level from Cohorts A1-A5 for evaluation of food effect. The selection of this dose level can be made prior to completion of all fasted SAD cohorts and will be based on a preliminary evaluation by the DRC of the available safety, tolerability, and PK data from selected Cohorts A1-A5. Subjects who complete participation in this selected cohort will be asked to return to the study site to be enrolled into the food-effect cohort (ie, Cohort A6), following a minimum of 7-day washout period since their last study drug dose. While Baseline evaluations will be conducted prior to dosing in Cohort A6, repeat assessment of all study eligibility criteria will not be performed. Returning subjects will retain their original subject number and randomized treatment assignment. After the Day 7 visit in the original cohort (from Cohort A1-A5), the study drug will be administered 30 minutes after the complete consumption of a high fat meal (approximately 50% calories from fat).

If there is an insufficient number of subjects from previous fasted SAD cohorts (ie, A1-A5), who are willing to participate in Cohort A6, then a separate Cohort A7 may be enrolled, comprising 6 new subjects meeting the study eligibility criteria, who will all receive ABI-4334. Cohort A7 will

involve a two-period crossover assessment of food effect (ie, Period 1: dosing under fasted or high fat-fed conditions; Period 2: dosing under condition opposite of Period 1), with a minimum 7-day washout period between dosing in Period 1 and Period 2, and a 7-day postdose follow-up in Period 2.

[figure not shown]

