3 GENERAL CONSIDERATIONS FOR DATA ANALYSES

Analysis results will be presented using descriptive statistics. For categorical variables, the number and percentage of subjects in each category will be presented; for continuous variables, the number of subjects (n), mean, standard deviation (SD) or standard error (SE), median, first quartile (Q1), third quartile (Q3), minimum, and maximum will be presented.

Summary tables will be presented by cohort and treatment. For cohort A7, summary tables will be presented fasting order (i.e. “fed,fasted” or “fasted,fed”).

No formal inference is planned in this study. Hence, no multiplicity adjustment is required.

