3.5.2.2 Cohort A7

The following periods will be defined for cohort A7:

- On-Treatment Period 1: Period 1 dose date
- Follow-Up Period 1: From Period 1 dose date +1 until Period 2 dose date.
- On-Treatment Period 2: Period 2 dose date.
- Follow-Up Period 2: From period 2 dose date +1 through end of study.

For each subject, end of study will be defined as completion of the last follow-up visit or premature study termination, or subject is lost-to-follow-up.

The study will end when the last subject completes the last visit of the follow-up period or is considered “lost to follow-up,” whichever is later.

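### For Cohort A7 the SAP exposure formula gives at least 8 days for two single doses, against a stated 1 day for Part A; a minor correction, with fed and fasted columns in the A7 safety tables as a cheap improvement

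*Combined protocol and SAP*

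**What the plan says.** SAP 4.3.1 defines duration as follows: "Total duration of exposure will be defined as the last dose date of study drug minus the first dose date plus 1". No cohort is excepted. The same section adds: "The expected total duration of exposure is 1 day for subjects in Part A and 8 days for subjects in Part B".

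Cohort A7 is the optional two-period food-effect cohort of Part A. It has 6 subjects, all on ABI-4334, with 3 dosed fed then fasted and 3 in the reverse order (SAP 1.4.1). SAP 1.2.1 describes the crossover "with a minimum 7-day washout period between dosing in Period 1 and Period 2" and sets no maximum gap.

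The SAP already splits A7 by period. Section 3.5.2.2 makes each On-Treatment Period a single dose date, for example "On-Treatment Period 2: Period 2 dose date". Section 3.5.3.2 counts study days within period, and 3.5.4 defines a Period 2 Baseline. Section 4.3.1 uses none of these.

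For table layout, SAP 3 states: "For cohort A7, summary tables will be presented fasting order", that is, by sequence. TEAEs run from first dose to end of study (5.1.5.1). Each subject counts once per summary, at the worst grade reached during the study (5.1.6). Graded laboratory results use each subject's worst post-Baseline grade (5.2.1.2).

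**The concern.** A formula and its expected result stand in the same section and disagree for one cohort. If the formula is programmed as written, the exposure table will show A7 subjects with a week or more of exposure after two single doses. At the minimum gap they would show the same 8 days as Part B subjects who were dosed on eight consecutive days.

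A second, softer issue concerns what the A7 safety tables can show. Every subject who completes A7 receives one fed and one fasted dose, so both sequence columns contain both conditions. A table that counts each subject once over the whole study cannot show which dose an event followed. That matters to anyone reading the study report for tolerability by meal state.

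**Working it through.** **Exposure.** Let F be the first dose date and L the last. The SAP formula is L − F + 1.

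Check against the plan's own figures:
- Cohorts A1–A5, one dose: 0 + 1 = 1 day. This agrees with the stated 1 day.
- Part B, Day 1 to Day 8: 7 + 1 = 8 days. This agrees with the stated 8 days.

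Cohort A7, both doses taken (7 is the SAP minimum; the longer gaps are assumed, since no maximum is given):

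| Days between doses | Formula result | Stated for Part A | Dosing days |
|---|---|---|---|
| 7 | 7 + 1 = 8 | 1 | 2 |
| 14 | 14 + 1 = 15 | 1 | 2 |
| 21 | 21 + 1 = 22 | 1 | 2 |

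If the washout is read as seven full drug-free days, the shortest gap is 8 and the result is 9. Only a subject who stops after Period 1 computes to 1 day. Applied within each period, the formula gives 0 + 1 = 1 day per period, and 1 + 1 = 2 dosing days in total.

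**What a sequence table can show.** Suppose k of the 6 subjects have an event. Each of the k had it after the fed dose only, the fasted dose only, or both. The number of different (fed, fasted) counts that fit is (k + 1)(k + 2)/2.
- 3/3 and 3/3: k = 6, so 7 × 8/2 = 28 possibilities, from fed 6/6 with fasted 0/6 to the reverse.
- 2/3 and 1/3: k = 3, so 4 × 5/2 = 10.
- 1/3 and 0/3: k = 1, so 2 × 3/2 = 3 (fed only, fasted only, or both).

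The same holds on average. Assume, for illustration only, a per-dose event probability of 0.30 fed and 0.10 fasted, independent and without carryover. Each sequence column then has probability 1 − 0.70 × 0.90 = 0.37, and the difference between conditions does not appear. These figures show what the layout cannot distinguish; they do not predict an effect.

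Numeric laboratory results and vital signs are shown by nominal visit, and ECG shifts by visit. Within a sequence column the period therefore identifies the condition, and these summaries are not affected by the pooling. Pharmacokinetic analyses are in a separate plan (SAP 6).

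**Baseline wording.** SAP 5.2.3 and 5.3 name the Period 2 Baseline for A7; 5.2.1.1 (treatment-emergent grade) and 5.5 (ECG shift) say only Baseline. The choice can change a result. Write grades as (Baseline, Period 2 Baseline, maximum after the Period 2 dose).
- (1, 0, 1): change 0 from Baseline, so not emergent, but +1 from Period 2 Baseline.
- (0, 1, 1): +1 from Baseline, but 0 from Period 2 Baseline.

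**Cohort A6.** Returning subjects keep their subject number and take a second dose at least 7 days after the first. If the first dose were taken to be the earlier fasted one, the exposure formula would again give 8 days or more. Protocol 10.1 (Baseline as predose on Day 1), the Baseline evaluations planned before A6 dosing, and Appendix 1b's own Day 1 all point to the A6 dose as the reference. The SAP does not say so.

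**The case against.** On exposure, the best defence is that the SAP already contains the remedy. Sections 3.5.2.2 and 3.5.3.2 work by period, and within a period the formula returns 1 day. Nor would dosing be hidden, because compliance is based on the amount administered and a dosing listing is planned (4.3.2). This limits the consequence, but it does not cure the text. Section 4.3.1 asks for a total duration from first to last dose and does not refer to the periods. Even on a per-period reading, it must say whether A7 is reported as 1 day per period or 2 in total.

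On the safety tables, a reader might infer that sequence columns breach the protocol. Protocol 10.4 says: "The safety and PK analyses will be presented according to the treatment received". Section 10.4.4 says: "Incidence of each body system and preferred term will be tabulated for each treatment". Section 3.2.2 speaks of a comparison "between fasted and fed treatments". The documents do not support that inference. The analysis sets in protocol 10.3 classify subjects by treatment received as against random assignment, SAP 1.4.1 randomises to ABI-4334 or placebo, and SAP 3.5.1 names those two as the study drugs. Treatment in 10.4 and 10.4.4 most naturally means the same thing. The wording in 3.2.2 belongs to a pharmacokinetic endpoint. The food-effect objective concerns pharmacokinetics only, and the primary safety endpoint is defined for each part, not by meal state.

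It also stands that presentation by sequence is an explicit choice, and that with 6 subjects the adverse-event, dosing and meal-time listings allow dated events to be traced to a dose by hand.

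A reader might likewise infer that the SAP leaves Period 2 grades and ECG shifts without a proper reference. That goes too far. SAP 3.5.4 gives a general Period 2 Baseline and a general Period 2 change rule for A7, which a careful programmer would apply. Only the cross-reference is missing.

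**Conclusion.** One part is wrong as written: for an A7 subject who takes both doses, SAP 4.3.1 yields at least 8 days where it states 1 and where dosing took place on 2 days. This rests only on the formula and the minimum washout.

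The pooling of fed-dose and fasted-dose events in the A7 TEAE and worst-grade tables is real, but it is a limitation of a chosen layout and not a departure from protocol 10.4 or 10.4.4. Separate columns are a worthwhile improvement. The Baseline and A6 items are clarifications of wording whose intended reading is already fairly clear.

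Overall the impact is minor. A7 is enrolled only if too few subjects return for A6, it has 6 subjects, its summaries are descriptive, and the pharmacokinetic food-effect analysis is untouched.

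**What to change.** 1. **Correct SAP 4.3.1.** For Cohort A7, compute exposure within each On-Treatment Period of 3.5.2.2, giving 1 day per period and 2 dosing days in total. Restate the expected figure for Part A to match. Cost: a sentence and a derivation.
2. **Improve the A7 safety tables.** Assign each A7 TEAE and treatment-emergent laboratory abnormality to the most recent dose by date and time. Add fed and fasted columns (up to 6 each, the same subjects) to the TEAE and maximum-grade tables. Cost: a derivation and two columns, for descriptive use in 6 subjects.
3. **Clarify Baseline.** In 5.2.1.1 and 5.5, refer to the A7 Period 2 Baseline of 3.5.4, as 5.2.3 and 5.3 already do.
4. **Clarify Cohort A6.** State that Baseline, Study Day 1, exposure and the start of the TEAE window are taken from the A6 dose.

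None of these needs new data, visits or subjects.

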4.3.2 Study Drug On-Treatment Compliance

The level of on-treatment compliance to the study drug will be determined by the total amount of study drug administered relative to the total amount of study drug expected to be administered during a subject's actual on-treatment period.

The level of on-treatment compliance for each study drug will be expressed as a percentage using the following formula:

$$\text{On-Treatment Compliance (\%)} = \left(\frac{\text{Total Amount of Study Drug Administered}}{\text{Total Amount of Study Drug Expected to be Administered on Treatment}} \right) \times 100$$

For subjects that prematurely discontinue, the denominator will be the total amount of study drug expected to be administered on treatment by the date of premature discontinuation.

Descriptive statistics for the level of on-treatment compliance with the number and percentage of subjects belonging to compliance categories (e.g. $\leq 80\%$, $> 80-90\%$, and $\geq 90\%$) will be provided by treatment and cohort for the Safety Analysis Set.

A by-subject listing of study drug administration will be provided by cohort and subject number in ascending order and visit in chronological order.

4.4 Meal Times and PK Sample Collection

Meal time information is collected in eCRF and will be listed for each subject. Listing will include date, start time, stop time, and percent of meal consumed.

PK plasma sample collection data is collected in eCRF and will be listed for each subject. Listing will include collection date/time, time of collection relative to dosing, and deviation from nominal sample time.

PK urine sample collection data is collected in eCRF and will be listed for each subject. Listing will include collection date/time, interval of collection relative to dosing, and total volume collected.

4.5 Medical History

Medical history collected at screening will be coded using the Medical Dictionary for Regulatory Activities (MedDRA) Version (v) 25.1.

Medical history will be summarized by preferred term (PT), treatment, and cohort. Subjects who report 2 or more medical history items that are coded to the same PT will be counted only once by the unique coded term in the summary. The summary will be provided for the Safety Analysis Set.

A by-subject listing of medical history will be provided by cohort and subject number in ascending order.

4.6 Demographics and Baseline Characteristics

Subject demographic variables (ie, age, sex, race, and ethnicity), Baseline characteristics (body weight [in kg], height [in m], and body mass index [BMI; in kg/m^2]) will be summarized by treatment and cohort using descriptive statistics for continuous variables and using number and percentage of subjects for categorical variables. The summary of demographic data will be provided for the Safety Analysis Set.

A by-subject demographic listing, including the informed consent date, will be provided by cohort and subject number in ascending order.

5 SAFETY ANALYSES

5.1 Adverse Events and Deaths

5.1.1 Adverse Event Dictionary

Clinical and laboratory adverse events (AEs) will be coded using the Medical Dictionary for Regulatory Activities (MedDRA) Version (v) 25.1. System organ class (SOC), high-level group term (HLGT), high-level term (HLT), preferred term (PT), and lower-level term (LLT) will be provided in the AE dataset.

5.1.2 Adverse Event Severity

Adverse events are graded by the Investigator as Grade 1, 2, 3, or 4 according to the toxicity criteria specified in the protocol. The severity grade of events for which the investigator did not record severity will be categorized as “missing” for tabular summaries and data listings. The missing category will be listed last in summary presentation.

5.1.3 Relationship of Adverse Events to Study Drug

Related AEs are those for which the investigator selected “Related” on the AE CRF to the question of “Relationship to Study Treatment” based on the his/her clinical assessment. Events for which the investigator did not record relationship to an applicable study drug will be considered related to study drug for summary purposes. However, by-subject data listings will show the relationship as missing.

5.1.4 Serious Adverse Events

Serious adverse events (SAEs) will be identified and captured as SAEs if the AEs met protocol-specified definitions of a SAE.

5.1.5 Treatment-Emergent Adverse Events

5.1.5.1 Definition of Treatment-Emergent Adverse Events

A treatment-emergent adverse event (TEAE) will be defined as any AE that has an onset date/time or worsening in severity from Baseline on or after the first dose date/time of study drug through end of study.

5.1.5.2 Incomplete Dates

If the onset date of the AE is incomplete and the AE stop date is not prior to the first dose date of any study drug, then the month and year (or year alone if month is not recorded) of onset determine whether an AE is treatment emergent. The event is considered treatment emergent if both of the following 2 criteria are met:

- The AE onset is the same as or after the month and year (or year) of the first dose date of study drug, and
- The AE onset date is the same as or before the month and year (or year) of the end of study.

An AE with completely missing onset and stop dates, or with the onset date missing and a stop date later than the first dose date of study drug, will be considered to be treatment emergent. In addition, an AE with the onset date missing and incomplete stop date with the same or later month and year (or year alone if month is not recorded) as the first dose date of any study drug will be considered treatment emergent.

5.1.6 Summaries of Adverse Events and Deaths

Treatment-emergent AEs will be summarized based on the Safety Analysis Set.

A brief, high-level summary of the number and percentage of subjects who experienced at least 1 TEAE in the categories described below will be provided by treatment and cohort. All deaths observed in the study will also be included in this summary. The number and percentage of subjects will be provided by SOC, PT, treatment, and cohort for each AE category and also by PT only in descending order of total frequency:

- TEAEs
- TEAEs by severity grade
- TEAEs related to study drug
- TE SAEs
- TE SAEs related to study drug
- TEAEs leading to study drug discontinuation
- TEAEs leading to study discontinuation
- TEAEs leading to death (ie, outcome of death)
- COVID-19 specific TEAEs
- COVID-19 specific TE SAEs

Multiple events will be counted only once per subject in each summary. Adverse events will be summarized and listed first in alphabetic order of SOC, and then by PT in descending order of total frequency within each SOC. For summary by severity grade, the most severe non-missing grade will be used for those AEs that occurred more than once in an individual subject during the study.

Data listings will be provided for the following:

- All AEs
- All treatment-related AEs
- All SAEs
- All treatment-related SAEs
- All AEs with severity of Grade 3 or higher
- All AEs leading to discontinuation of study drug
- All AEs leading to discontinuation of study
- All AEs leading to death (ie, outcome of death)
- All Deaths

5.2 Laboratory Evaluations

Laboratory data collected during the study will be analyzed and summarized using both quantitative and qualitative methods based on the Safety Analysis Set. The lab values that are below LLOQ or above the upper LOQ will be listed as such, and the closest imputed value will be used for the purpose of calculating summary statistics as specified in [Section 3.3](#).

A by-subject listing for laboratory test results will be provided by cohort, subject number, and visit in chronological order for hematology, serum chemistry, coagulation and urinalysis separately. Values falling outside of the relevant reference range and/or having a United States National Institutes of Health Division of AIDS (DAIDS) severity grade of 1 or higher will be flagged in the data listings, as appropriate.

